2.2 Primary and secondary endpoints

Primary endpoints

Muscle soreness

A visual analogue scale (VAS) is used for the quantitative assessment of muscle soreness. The muscle soreness of the test subjects is measured on both ventral thighs in 90° knee flexion within 2 seconds. Participants perform a squat at a 90-degree angle and use a hand-held glide scale to choose a value between 0 and 10 cm, with 0 representing no discomfort and 10 representing maximum discomfort. This scale is designed without visible numerical indicators to minimize repetition bias. Measurements are taken during baseline and 24, 48, and 72 hours after the intervention. The examination staff records the selected value in centimetres to document the level of the muscle soreness symptoms felt ventrally.

Inflammation levels

The general inflammation values are determined on the basis of 3 parameters. These are the blood sinking rate, the C-reactive protein and the creatine kinase. These parameters are determined by means of a venous blood draw.

Muscle swelling

Swelling of the ventral thigh muscles is performed using ultrasound diagnostics. The test subjects are in a lying position. Subsequently, a cross-sectional image of the thigh muscles is created and the distance from the femur to the outer boundary of the muscles is measured.

Maximum voluntary isometric muscle contraction

This parameter is measured using an ergometer chair in 90° hip flexion. The test subjects have to try to stretch their thigh as much as possible for 3 seconds. The maximum deflection is used to determine the maximum voluntary isometric muscle contraction.

Secondary endpoints

Superficial skin temperature

The skin temperature of the thighs is measured using the iButton system. The sensors are glued to the skin and continuously measure the temperature of the skin. The data from the sensors is then read out on a computer. This measurement is started during the baseline survey, for the duration of the muscle soreness protocol, and up to 20 minutes after the muscle soreness protocol.

Thermal Perception

The thermal perception of the participants is recorded immediately after exposure to cold using the standardized Thermal Perception Scale (-4 to +4). This scale ranges from -4 ("extremely cold") to +4 ("extremely warm"), with 0 being considered neutral. The evaluation is carried out as a subjective self-assessment in order to document the individual temperature perception. Participants will be informed about the scale in advance. Since this is a purely subjective assessment, there is no risk for the participants.

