Investigation procedures	
Subject recruitment
 
The test subjects are recruited at the University of Physiotherapy THIM in Landquart and the University of Applied Sciences and Arts Southern Switzerland in Landquart.
 
The subject information and the declaration of consent are given to the test subjects. In the subject information there is a checklist that the test persons must fill out in order to check the inclusion and exclusion criteria.
 
If the subjects agree with the information, have completed the checklist and signed the consent, they will be summoned to make an appointment for the measurement.
 
Investigation Protocol
 
As soon as the signed consent of the test person has been received and an appointment has been made, the following procedure is followed. The anthropometric data of the subjects will be collected and group randomization will be carried out. Afterwards, the baseline measurements are carried out and the measurement of the skin temperature is started. Then the muscle soreness protocol (6 x 12 to 15 one-legged knee extensor protocol with a 2-minute break between sets) is completed. Cooling group A then receives the first 20-minute cooling of the thigh group.
 
Cooling group B and the control group leave the laboratory 20 minutes after the muscle soreness protocol. The measurement of skin temperature is stopped within all groups 20 minutes after the muscle soreness protocol.
 
Cooling group B begins cooling the thigh muscles 24 hours after the muscle soreness protocol. Both cooling groups perform cooling of the thigh muscles 3 x / day for the duration of the data collection (up to 72 hours according to the muscle soreness protocol).
 
At intervals of 24, 48 and 72 hours, the primary endpoints of the study are collected again. These include: muscle soreness, inflammation levels, muscle swelling, maximum voluntary isometric contraction of the thigh muscles.
 
Measurement of sore muscles
 
The level of ventrally felt muscle soreness symptoms is measured using a VAS scale (0 – 10 cm). The test subjects rate the perceived muscle soreness in both ventral thighs in a 90° knee flexion position. The measurement takes place during the baseline measurement and, 24 hours, 48 hours and 72 hours after the intervention.
 
Inflammation levels
 
The inflammation values (blood sedimentation rate, C-reactive protein, creatine kinase) are determined by venous blood sampling. The measurement takes place during the baseline measurement and, 24 hours, 48 hours and 72 hours after the intervention.
 
Muscle swelling
 
The measurement of muscle swelling of the quadriceps femoris muscle is carried out by ultrasound measurement. The measurement is carried out in a resting position and a cross-section of the muscle is recorded. The measurement takes place during the baseline measurement and, 24 hours, 48 hours and 72 hours after the intervention.
 
Measurement of maximum voluntary isometric thigh muscle contraction (MVIC)
 
MVIC is performed on an ergometer chair for biomechanical measurements and is given in kg. The measurement takes place during the baseline measurement and, 24 hours, 48 hours and 72 hours after the intervention.
 
Surface temperature
 
The surface temperature is measured using the iButton system. These sensors are glued to the skin for the duration of the measurement. The button sensors store the current temperature information and can then be read out via a computer. These measurements are started during the baseline survey, for the duration of the muscle soreness protocol, and up to 20 minutes after the muscle soreness protocol.
 
Detection of thermal perception
 
The thermal perception of the participants is recorded immediately after exposure to cold using the standardized Thermal Perception Scale (-4 to +4). This scale ranges from -4 ("extremely cold") to +4 ("extremely warm"), with 0 being considered neutral. The evaluation is carried out

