2.3 Investigation design

This study is a single-center, randomized, controlled trial with 3 arms. After the subjects have been admitted to the examination, they are divided into one of the 3 groups.

Group A: immediate cooling according to the muscle soreness protocol

Group B: delayed cooling according to the muscle soreness protocol (24 hours delayed)

Group C: Control group

This examination is a clinical trial of risk category A.

Group A: immediate cooling

In this group, cooling starts immediately after the muscle soreness protocol. Cooling is carried out 3 x /day both on the day of the muscle soreness protocol and for a period of 72 hours. Both thighs are cooled with the "Cold Hot Maxi Pack" from Axanova for a period of 20 minutes.

Cooling log: Day 1 (muscle soreness log, 3x/day), Day 2 (3x/day), Day 3 (3x/day), Day 4 (3x/day)

Group B: delayed cooling

In this group, cooling starts 24 hours after the sore muscle protocol. Cooling is also carried out 3 x /day for a period of 72 hours. Both thighs are cooled with the "Cold Hot Maxi Pack" from Axanova for a period of 20 minutes.

Cooling log: Day 1 (muscle soreness log, no cooling), Day 2 (3x/day), Day 3 (3x/day), Day 4 (3x/day).

Group C: Control group

This group receives according to the muscle soreness protocol and will not receive any cooling intervention, nor any other intervention, for the entire period thereafter.

Sore muscle protocol

To induce sore muscles, the test subjects perform one-sided, 6 times 12 – 15 knee extensors on an ergometer chair. They straighten and bend the knee as far as possible. They repeated the exercise 5 more times after a 2-minute break (a total of 6 rounds). The movement sequences are observed and corrected if necessary. A similar protocol has already been successfully used in the literature to induce muscle soreness (Ruas et al 2022, Comparison between eccentric-only and coupled concentric-eccentric contractions for neuromuscular fatigue and muscle damage). In order to increase the significance of the investigation, the subjects are asked not to carry out any additional interventions during the experimental phase.

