a TANITA-TBF 611 scale (Tokyo, Japan). The estimate of the percentage of lower body fat was chosen because the cold pack was applied to the thigh, which mainly affects the lower extremities. Recovery parameters (see Exact Measurement Method and Primary and Secondary Endpoints) are assessed in the same order for each measurement: (1) Inflammation Scores, (2) Muscle Swelling, (3) Soreness, (4) Maximum Voluntary Isosomic Muscle Contraction. The measurement method and the equipment used for each specific result are described in Chapter 3.2.

Randomization

The randomization of the subjects will take place on the day of the baseline measurement by drawing a lot. It is ensured that the same number of tickets are available for each intervention group (5 tickets per group) and test subjects. If the number of subjects in a group exceeds one third of the total number of subjects, the lots of this group will be removed. In order to ensure the equality of the groups in terms of covariates and gender, the composition of the groups is monitored. As soon as half of a group consists of male or female subjects, the tickets for this group are removed for future subjects of the same sex.

The tickets are made of folded paper with the numbers 1, 2 or 3 on them and are placed together in a container. The drawing of the lots is carried out by the test persons themselves. After the draw, the subjects hand over the unread ticket to the study director, who assigns them to a group.

Blinding

Since cold applications are tested in this study, blinding is not possible.

Sore muscle protocol

To induce muscle soreness, a one-legged knee extensor protocol is used, which has already been used (Ruas et al., 2022). Participants will be instructed to straighten and bend their knee for 6 sets for 12 – 15 reps, with 2 minutes rest between sets. During the 2-minute break, the participants are allowed to sit on the chair. The execution of the knee extensor protocol is visually observed by an examiner. Verbal corrections of the execution can be given by the examiner. However, no verbal encouragement is given. All training sessions are carried out in the morning. If a participant is unable to perform all the repetitions of a set due to extreme fatigue or maximum effort, the set can be stopped and a new set can be started after the rest period. However, at least 12 repetitions per set must be performed. Otherwise, this will be considered an abandonment.

Intervention

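### The exercise is described as one-legged, but soreness, the endpoint used for sizing, is one rating over both thighs, and no leg is named for ultrasound or strength

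*Combined protocol and SAP*

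**What the plan says.** **Exercise.** Section 2.3 states: "To induce sore muscles, the test subjects perform one-sided", with the knee in the singular and six rounds in all. Section 3.3 states: "To induce muscle soreness, a one-legged knee extensor protocol is used", again with one knee and six sets. The synopsis (Investigation procedures) also calls it one-legged. No section says which leg is used, or that the other leg is exercised as well.

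**Soreness.** Section 2.2 states: "The muscle soreness of the test subjects is measured on both ventral thighs in 90° knee flexion within 2 seconds". It continues: "Participants perform a squat at a 90-degree angle and use a hand-held glide scale to choose a value between 0 and 10 cm". Staff record that one value. The synopsis agrees on the site: "The test subjects rate the perceived muscle soreness in both ventral thighs in a 90° knee flexion position". There is no per-leg score and no rule for combining two scores.

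**Swelling and strength.** For ultrasound, section 2.2 says "a cross-sectional image of the thigh muscles is created and the distance from the femur to the outer boundary of the muscles is measured". For MVIC it says "The test subjects have to try to stretch their thigh as much as possible for 3 seconds". Neither names a side, and neither requires the same side at each visit.

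**Cooling.** In groups A and B both thighs are cooled (sections 2.3 and 3.3), with one pack per thigh (section 2.4).

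**Cross-reference.** Section 3.3 twice sends the reader to Chapter 3.2 for measurement methods and equipment. Section 3.2 covers recruitment, screening and consent and says nothing about the leg.

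**The concern.** Read literally, the plan exercises one thigh and rates two. An unexercised thigh has no exercise-induced soreness for cooling to reduce, so including it in a single rating can shrink the contrast between cooled and control participants. Soreness is the endpoint behind the sample size in section 4.1, and the planned margin is thin: power for A against control is 83% against a target of 80%.

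The silence on the leg for ultrasound and MVIC is a lesser matter. On its own it is missing detail. It belongs here because those two primary endpoints also depend on which leg is measured, and because section 3.3 rules out blinding, so an unfixed choice of leg could be made with the arm known. ESR, CRP and creatine kinase come from venous blood and are not affected.

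**Working it through.** **Inputs, all from section 4.1.** Control mean 4.72; treatment means 2.21 (A) and 1.87 (B), so differences of 2.51 and 2.85; common SD 2.1; 13 evaluable per arm; two-sided alpha 0.05 with no Bonferroni divisor; two-sample equal-variance t-test.

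**Step 1: reproduce the plan.** Power comes from the noncentral t with 2 × 13 − 2 = 24 degrees of freedom and noncentrality δ / (σ√(2/13)).
- A: 2.51 / (2.1 × 0.392) = 3.05, power 0.832. The plan gives 0.83233.
- B: 2.85 / (2.1 × 0.392) = 3.46, power 0.913. The plan gives 0.91287.

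Both figures reproduce. The calculation is sound; the difficulty is in how the endpoint is defined.

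**Step 2: dilution, as assumed scenarios.** The documents give no dilution factor. Suppose that only one leg is exercised, that the planning values describe an exercised thigh, and that a participant's single rating is the average of the two thighs. The difference then halves:
- A: 2.51 / 2 = 1.255 cm
- B: 2.85 / 2 = 1.425 cm

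The SD of the average depends on the non-sore thigh's SD, s, and on its correlation r with the sore thigh:

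SD = ½ √(2.1² + s² + 2 r × 2.1 × s)

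| s (assumed) | r (assumed) | SD of the rating | Power, A | Power, B |
|---|---|---|---|---|
| 0 | – | ½√4.41 = 1.05 | 0.832 | 0.913 |
| 1.05 | 0 | ½√5.5125 = 1.174 | 0.744 | 0.843 |
| 1.05 | 0.5 | ½√7.7175 = 1.389 | 0.599 | 0.709 |
| 2.1 | 0 | ½√8.82 = 1.485 | 0.543 | 0.651 |
| 2.1 | 0.5 | ½√13.23 = 1.819 | 0.393 | 0.483 |
| 2.1 | 1 | ½√17.64 = 2.1 | 0.310 | 0.383 |

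In the first row the difference and the SD both halve, so the standardised effect is unchanged (1.255 / 1.05 = 2.51 / 2.1 = 1.195) and nothing is lost. In the last row the difference halves and the SD does not shrink at all.

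**Step 3: the case without averaging.** If participants simply report the side that hurts, the difference stays at 2.51 and power at 0.832.

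**Step 4: after the fix.** With the rating confined to an exercised thigh, the planned 13 evaluable and 15 enrolled per arm (45 in total) stand, with power of 83.2% and 91.3%. This holds provided the planning means and SD describe an exercised thigh, which section 4.1 does not say.

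**The case against.** The strongest answer is that both legs may be exercised, one after the other, and that one-legged describes only how the movement is done. Cooling both thighs and rating both thighs fit that reading, and the text reads as a rough translation. If it is right, the dilution disappears and a wording error remains. This stands as a possibility. But no section says that the second leg is exercised, and section 2.3 counts six rounds in total for one knee. The passages need reconciling whichever reading is intended.

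A second answer is that averaging is speculative. Section 2.2 asks for one value for soreness felt at the front of the thighs during a squat, and a participant may well report the sore side. That also stands, and it is why no loss belongs in the range. The synopsis might instead mean one rating per thigh, but then no rule says which value, or what combination, enters the ANOVA in section 4.1.

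Two stronger readings are tempting. A reader might infer that the trial's power is really about 31%. That figure needs the SD to stay at 2.1 after averaging, for example because the non-sore thigh is as variable as the sore one and perfectly correlated with it. A thigh that is not sore would more naturally sit near zero with little spread, which moves power back towards 83%. A reader might also infer that swelling and strength will be taken on an undamaged leg. The documents do not say this; they only fail to name the leg.

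Randomisation makes a directional bias from the rating rule less likely, but it does not restore lost sensitivity.

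**Conclusion.** The contradiction is plain in the text: one leg exercised, two thighs rated with one value, two thighs cooled, and no leg fixed for ultrasound or MVIC. If only one leg is exercised, following the stated soreness rule can weaken the comparison on which the trial was sized.

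The size of that loss cannot be settled from the documents. For A against control it runs from none (83%) to a fall to 31%, with 74–60% if the non-sore thigh has SD 1.05 and 54–39% if it has SD 2.1, each at correlations from 0 to 0.5. These figures assume averaging, planning values that describe an exercised thigh, and the plan's own t-test at 13 per arm. They show how sensitive the design is; they do not predict the trial's power. The point is worth correcting because the contradiction is certain and the correction is cheap, not because a large loss has been shown.

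**What to change.** Reconcile sections 2.2, 2.3 and 3.3, and the synopsis with them, on which leg or legs are exercised.

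- **If one leg is exercised:** choose it by one rule for all arms, set before allocation, and record it. Take the VAS, the ultrasound and the MVIC on that leg at baseline, 24, 48 and 72 hours, with the VAS instruction asking for soreness in that thigh only.
- **If both legs are exercised in turn:** correct the exercise text to say so, and name one pre-specified index leg for ultrasound and MVIC at all four time points. The both-thigh VAS can then stand. An index leg avoids doubling the ultrasound and MVIC measurements within the 30-minute follow-up visits.

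In either case, replace the pointer to Chapter 3.2 with one to the section that describes the measurements. The blood markers need no change, and this point asks for no change to the cooling.

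The cost is protocol wording and one CRF field for the leg. It adds no visits, and the planned 45 participants need not change on this account.

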2.3 Investigation design

This study is a single-center, randomized, controlled trial with 3 arms. After the subjects have been admitted to the examination, they are divided into one of the 3 groups.

Group A: immediate cooling according to the muscle soreness protocol

Group B: delayed cooling according to the muscle soreness protocol (24 hours delayed)

Group C: Control group

This examination is a clinical trial of risk category A.

Group A: immediate cooling

In this group, cooling starts immediately after the muscle soreness protocol. Cooling is carried out 3 x /day both on the day of the muscle soreness protocol and for a period of 72 hours. Both thighs are cooled with the "Cold Hot Maxi Pack" from Axanova for a period of 20 minutes.

Cooling log: Day 1 (muscle soreness log, 3x/day), Day 2 (3x/day), Day 3 (3x/day), Day 4 (3x/day)

Group B: delayed cooling

In this group, cooling starts 24 hours after the sore muscle protocol. Cooling is also carried out 3 x /day for a period of 72 hours. Both thighs are cooled with the "Cold Hot Maxi Pack" from Axanova for a period of 20 minutes.

Cooling log: Day 1 (muscle soreness log, no cooling), Day 2 (3x/day), Day 3 (3x/day), Day 4 (3x/day).

Group C: Control group

This group receives according to the muscle soreness protocol and will not receive any cooling intervention, nor any other intervention, for the entire period thereafter.

Sore muscle protocol

To induce sore muscles, the test subjects perform one-sided, 6 times 12 – 15 knee extensors on an ergometer chair. They straighten and bend the knee as far as possible. They repeated the exercise 5 more times after a 2-minute break (a total of 6 rounds). The movement sequences are observed and corrected if necessary. A similar protocol has already been successfully used in the literature to induce muscle soreness (Ruas et al 2022, Comparison between eccentric-only and coupled concentric-eccentric contractions for neuromuscular fatigue and muscle damage). In order to increase the significance of the investigation, the subjects are asked not to carry out any additional interventions during the experimental phase.

2.4 Investigation intervention

The repeated cold applications are carried out by the test subjects independently at home. For this, the test subjects receive 6 cold packs to take home (CE-certified Axanova Cold Hot Pearls Maxi Pack, Axanova AG). One cold pack is applied per thigh (2 packs per cooling session). The packs must be placed in a chest freezer/freezer compartment 1 hour before use. After the minimum cooling time has expired, the cold packs are placed on the thighs for 20 minutes with the fleece side down (skin contact). There must be at least 4 hours between cold applications. The cold packs may only be applied to the skin, without any additional pressure. The 20-minute cold application is described by the manufacturer Axanova as follows. We do not change the duration of application or form. The applications 24, 48 and 72 hours after the muscle soreness protocol are carried out by the test subjects at home and documented with a photo. Study participants upload these images directly to a designated cloud-based folder via a secure, password-protected link. This ensures that the data is transmitted and stored in encrypted form. When the intervention is carried out in the laboratory by the study staff, the temperature of each

cold pack is checked using an infrared thermometer to document possible temperature differences. This measurement is used to record potential variations in the cooling effect without influencing the application of the cold pack.

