3.3 Investigation procedures

Investigation duration:

Subject to EC approval in 2024.

Recruitment period: January 2025

Conduct of the study: February - March 2025

Statistics and writing of the article: April – July 2025

Individual Investigation duration for each participant

Phase	Content	Time
Recruitment	Handing out patient information & consent, explanation of the experiment	30 min
Experiment Day 1	Anthropometry, baseline measurement, muscle soreness protocol (cooling: group A)	60 min
Experiment Day 2	Follow-up measurement 24 hours (Cooling: Group A and Group B)	30 min
Experiment Day 3	Follow-up measurement 48 hours (Cooling: Group A and Group B)	30 min
Experiment Day 4	Follow-up measurement 72 hours (Cooling: Group A and Group B)	30 min
Total time required per subject		180 min

Recruitment

As soon as the potential test subjects show interest in the study and arrive at the laboratory in Landquart, they are sent to the study director. If he is not present or available at that time, interested parties are asked to appear on another day.

The head of the study explains the procedure, the tests carried out, the risks and possible inconveniences. In addition, it is explained that participation is voluntary and that withdrawal is possible at any time, without giving reasons, without this having a negative impact on future care. The test subjects then receive the test subject information, which describes the examination in detail and in an understandable way. The document also contains a checklist that must be completed. The declaration of consent is also provided and must be signed and returned by the Director of Studies before the start of the programme. The doctor checks the completed checklist and confirms the consent.

Baseline measurements

The room temperature and relative humidity are determined at the beginning of each measurement day (Voltcraft MT52 digital multimeter, Hirschau, Germany). Baseline measurements include demographic data (age, gender, height). Anthropometric features at the beginning of the study included height (GPM Stadiometer, Zurich, Switzerland), body mass, and body fat percentage estimation. Body mass and lower body fat percentage were measured using

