The subjects in group A (immediate cooling) receive the first cooling on the two thighs immediately after the end of the muscle soreness protocol. This cooling is carried out in the supine position. After this application, you can leave the laboratory and the measurement of the skin temperature is stopped.

Group B (delayed cooling) and group C (control group) do not receive any cooling (group B) or any intervention (group C) immediately after the muscle soreness protocol. However, you will also need to spend 20 minutes lying on your back in the lab before the skin temperature measurement is completed.

Follow-up measurements

Follow-up measurements will be taken for each measurement in the same order as for the baseline measurement ((1) Inflammatory markers, (2) Muscle swelling, (3) Soreness of muscles, (4) Maximum voluntary isometric contraction). The follow-up measurements take place 24, 48, and 72 hours after the muscle soreness protocol in the laboratory in Landquart.

The measurement method and the equipment used for each specific result are described in Chapter 3.2.

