5.2.1 Foreseeable adverse events and anticipated adverse device effects

Predictable AEs during the application of the MD.

Type of event	Description	Mitigation or Treatment Measures	Probable incidence
Skin irritation or redness	Localized erythema or irritation at the application site due to pressure or cold.	use protective materials; apply soothing creams or gels if necessary.	Medium
Pain or discomfort	Temporary pain or discomfort during or after application due to refrigeration.	Ask participants to report pain.	Small
Decreased local sensitivity	Temporary numbness or decreased sensitivity due to exposure to cold.	inform participants about this possibility; Avoid prolonged use to prevent complications.	Medium
Slight swelling or edema	Localized swelling due to prolonged cooling or improper use.	Monitor application time; elevate the affected area; Reduce application time for subsequent applications.	Small

No SAEs are expected.

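### Home cooling and laboratory follow-up share the nominal times 24, 48 and 72 h with no fixed order or minimum interval, so a soreness difference from control could partly be short-lived numbing.

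*Combined protocol and SAP*

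**What the plan says.** **Cooling.** The Synopsis (Investigation procedures) states: "Both cooling groups perform cooling of the thigh muscles 3 x / day for the duration of the data collection". Section 2.4 places the later sessions outside the laboratory: "The applications 24, 48 and 72 hours after the muscle soreness protocol are carried out by the test subjects at home". The only spacing rule there is "There must be at least 4 hours between cold applications". For the delayed arm the Synopsis says: "Cooling group B begins cooling the thigh muscles 24 hours after the muscle soreness protocol"; section 2.3 agrees.

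**Measurement.** Section 3.3 (Follow-up measurements) says: "The follow-up measurements take place 24, 48, and 72 hours after the muscle soreness protocol in the laboratory in Landquart". It also fixes a sequence: "Follow-up measurements will be taken for each measurement in the same order as for the baseline measurement", that is, blood markers, ultrasound, soreness, then MVIC. Cooling has no place in that sequence. The schedule table in 3.3 puts both on one line, for example "Follow-up measurement 24 hours (Cooling: Group A and Group B", without clock times or visit windows.

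**Time origin.** The Synopsis and section 2.2 count the soreness assessments from the intervention. Section 3.3 counts them from the muscle soreness protocol.

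**Expected effect of cold.** The table in 5.2.1 lists "Temporary numbness or decreased sensitivity due to exposure to cold" and rates its probable incidence as medium. Under 2.2, soreness is self-rated on both ventral thighs; under 2.3, both thighs are cooled; under 3.3, nobody is blinded.

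**The concern.** Soreness on the VAS is a primary endpoint and the one used to size the trial. It is meant to measure recovery. If some participants in the cooling arms come to the laboratory after a session that morning, their rating may carry a temporary loss of sensation. The control group is never cooled, so an effect of this kind can fall only on the cooling arms, and on the VAS it would favour them. The plan as written allows this without any protocol deviation, and the analysis could not separate it from recovery because no section asks for the time since the last application at the visit.

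The second hypothesis, immediate against delayed cooling, is touched as well. The 24 h visit is the only post-exercise assessment at which group A has been cooled and group B should not have been, and group B's first session carries that same nominal time.

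**Working it through.** **1. Is an order or interval stated anywhere?**

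| Rule in the plan | What it governs | Does it order cooling against assessment? |
|---|---|---|
| 2.4, at least 4 h | One cold application to the next | No |
| 3.3, Follow-up measurements | The four measurements among themselves | No |
| 3.3, schedule table | Which days have a visit and cooling | Layout only: measurement named first, cooling in brackets |
| 2.4, photo of home sessions | Documentation of the session | No; nothing says it is linked to the visit |

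On day 1 the table's layout matches the real sequence, so measure-then-cool is a plausible intention for days 2 to 4. Even so, with three sessions a day it would not exclude an earlier home session on the visit day: group A at 24 h, groups A and B at 48 and 72 h.

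**2. The plan's own figures (section 4.1).** Inputs: SD 2.1, 13 per arm, two-sided alpha 0.05 with divisor 1, differences 2.51 (A) and 2.85 (B) from control.

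- Standard error = 2.1 × √(2/13) = 0.824; degrees of freedom = 2 × 13 − 2 = 24; critical t = 2.064.
- Noncentrality = difference / standard error: 2.51/0.824 = 3.05 and 2.85/0.824 = 3.46.
- Power from the noncentral t distribution: 0.8323 and 0.9129. The plan states 0.83233 and 0.91287, so both reproduce.

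**3. Illustration of the bias.** The documents give neither size nor duration for an effect of numbness on the VAS, so what follows is assumption. Suppose cooling has no true effect on recovery, and a share f of a cooled arm is rated b cm lower because of recent cooling. The apparent difference from control is b × f. The variance in the cooled arm becomes 2.1² + b² × f × (1 − f), and the pooled SD is the square root of the mean of that and 2.1². The same t-test then gives:

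| b (cm) | f | Apparent difference (cm) | Pooled SD | Noncentrality | Chance of p < 0.05 | Share of planned 2.51 cm |
|---|---|---|---|---|---|---|
| 0 | – | 0 | 2.100 | 0 | 5% | 0% |
| 0.5 | 0.25 | 0.125 | 2.106 | 0.15 | 5.2% | 5% |
| 1.0 | 0.5 | 0.5 | 2.130 | 0.60 | 8.9% | 20% |
| 0.5 | 1 | 0.5 | 2.100 | 0.61 | 9.0% | 20% |
| 1.0 | 1 | 1.0 | 2.100 | 1.21 | 21.4% | 40% |

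These are single-time-point t-tests, as in the sample size calculation. The planned analysis is a repeated-measures ANOVA, so they show the order of magnitude and not the error rate of the final test.

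**The case against.** The strongest reply is that the plan implies measurement first. The table names it first, and a 30-minute visit for four measurements hardly leaves room for a 20-minute application. Travel from home, the blood draw and the ultrasound always come between a home session and the soreness rating. No section links reduced local sensitivity to soreness rated in a squat. All of this stands as a reason to expect a modest effect. None of it is a rule, and none of it excludes a session earlier that day.

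A reader might infer more than the documents support:

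- **That group B is already cooled at its 24 h rating.** Its cooling is defined to start at 24 h. Being cooled before the rating would need a late visit or an early start. With no visit window this is possible, but it is secondary.
- **That ratings are taken minutes after an application.** Travel and the two preceding procedures argue against this.
- **That MVIC is biased in favour of cooling.** No section supports a direction. The argument does not reach the blood markers or ultrasound either.
- **That the home and laboratory descriptions of cooling conflict.** The table lists the days of cooling and does not place it in the laboratory. The laboratory clause in 2.4 fits group A's first session. What is missing is the order.
- **That the error rate is far higher than shown.** Larger figures need a bigger shift than 1.0 cm, and the upper figures in the table already assume that every cooled participant is affected.

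**Conclusion.** The point holds as a gap in the design with a definite direction for the VAS. Cooling and assessment share nominal times, no order or minimum interval is set, and the protocol itself expects temporary numbness in the region being rated. A VAS difference between a cooling arm and control at 24, 48 or 72 h could therefore be partly short-lived numbing.

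The size is unknown. Under the assumed lowering of 0.5 to 1.0 cm, the false-positive chance goes from 5% to between 9% and 21% if every cooled participant is affected, and to about 5% to 9% if a quarter (0.5 cm) to half (1.0 cm) are. This rests on SD 2.1, 13 per arm, no true effect and one time point. The group B question at 24 h is a matter of making its status explicit. The change should be made because it is cheap, and because an interval that was not recorded cannot be recovered at analysis.

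**What to change.** 1. Reconcile the Synopsis and sections 2.2, 2.3, 2.4 and 3.3 on the order of cooling and assessment and on the time origin (soreness protocol or intervention).
2. State in 3.3 one fixed order of assessment relative to cooling that applies to all participants. The sponsor chooses it, so that soreness is not rated shortly after an application and group B's 24 h assessment precedes its first session.
3. Record the clock time of the last application on the CRF at each visit.
4. Add to 4.1 a VAS sensitivity analysis that uses time since last cooling.

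Number, length and spacing of applications are left to the sponsor.

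The cost is one participant instruction, one CRF field, a short addition to 3.3 and 4.1, and slightly less freedom in the timing of home sessions on visit days. Section 3.3 puts the exercise session in the morning, so visits 24, 48 and 72 h later also fall in the morning. Group A already has all its day 1 applications after a morning session, so such a day is workable under the existing 4 h spacing.
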